3.3 ENHANCED MINDFULNESS INTERVENTION (IMMEDIATE INTERVENTION GROUP)

After patients and their caregivers complete the in-person session (see *Experimental Design* in the Research Project Narrative for additional details), they will be provided with structured mindfulness exercises to practice at home. They will be asked to practice at least one mindfulness activity (out of 5 primary choices) at least 4 out of 7 days per week, with an ideal goal of daily practice. The home-based practices are tailored based on the participant's developmental stage, though each age group shares three common practices (i.e., Loving Kindness, Body Scan, and Mindful Breathing). Below is a brief description of the at-home practices that will be offered to participants, arranged by age group. Flexibility is permitted within the intervention protocol to adapt exercises or offer alternative practices for patients when needs arise (e.g., cognitive and/or verbal limitations, physical limitations). This will be addressed on a case-by-case basis with participants during the initial in-person session, at which point adaptations/alternatives will be provided. Patients and caregivers will be allowed to choose among the mindfulness exercises provided (the research team will track their choices via a tracking sheet). All materials needed to complete these exercises will be provided to participants.

3.3.1 Home-Based Mindfulness Practices for Caregivers

Home-based practices for caregivers will primarily consist of guided mindfulness meditations via audio recordings. This will include brief (i.e., 5-minute) and extended (i.e., 15-20-minute) formats. Audio files (.mp3 files) will be provided to caregivers immediately following or during the in-person session and can be downloaded to a smart phone, tablet, or computer. Mp3 players will be available for any participant who does not have access to a personal device through which these files can be accessed. Descriptions of these exercises are available in Study Instrument 4.

3.3.2 Home-Based Mindfulness Practices for Adolescents and Young Adults (13-24 years old)

Home-based practices for adolescents will be multi-format in nature. Exercises aim to increase awareness of emotional and physical experiences, and enhance attunement to environmental stimuli. Although each of these exercises can be completed independently, they can also be completed with the company of a caregiver. Descriptions of these exercises are in Study Instrument 5.

3.3.3 Home-Based Mindfulness Practices for Youth (8-12 years old)

Home-based practices for pre-adolescent youth will be multi-format in nature. Exercises aim to increase awareness of emotional and physical experiences, and enhance attunement to environmental stimuli. Exercises are completed independently or with a caregiver.

Reinforcement (e.g., tangible items like stickers, praise, positive attention) can be paired with these exercises to increase engagement in this age group. Descriptions of these exercises can be found in Study Instrument 6.

3.3.4 Home-Based Mindfulness Practices for Children (5-7 years old)

Mindfulness practices for young children are interactive and engaging. These exercises are intentionally game-like and utilize reinforcers (e.g., tangible items, positive caregiver attention) to help sustain participation and patient enjoyment. Tangible reinforcers (e.g., stickers) will be provided in the mindfulness toolkit. All exercises should be completed with a caregiver and offer mutual benefit such that a caregiver would not have to complete a separate practice. Descriptions of these exercises are in Study Instrument 7.

3.4 COST AND COMPENSATION

3.4.1 Costs

NIH does not bill health insurance companies or participants for any research or related clinical care that participants receive at the NIH Clinical Center. If some tests and procedures performed outside the NIH Clinical Center, participants may have to pay for these costs if they are not covered by insurance company. Medicines that are not part of the study treatment will not generally be provided or paid for by the NIH Clinical Center.

3.4.2 Compensation

Participants (each child and each parent/caregiver) will receive compensation (\$20) for completing each set of questionnaires to thank them for their time and effort spent participating in this study. The maximum compensation that any participant can receive is \$60 (questionnaires at baseline, 8 weeks and 16 weeks). Funds will be distributed in accordance with the Clinical Center's Research Volunteer system, such that participants can have the money directly deposited to a bank account or have a check mailed to them.

In addition, each parent-child dyad will receive a mindfulness toolkit as part of this study, which will provide them with all the necessary supplies to practice the mindfulness exercises outside the clinic. Because we anticipate that some families will be away from their home environment while they participate in this project, it is essential that all equipment be provided to families. This will include pragmatic supplies to complete exercises (e.g., art supplies for art-based mindfulness exercises such as Mandalas, bubbles, copyrighted audio files, headphones) in addition to tools to enhance their experience (e.g., eye pillow, meditation mat). Collectively, these supplies will cost approximately \$100 per dyad. These costs are covered by a grant through the St. Baldrick's Foundation, awarded to [name] in support of this study.

3.4.3 Reimbursement

This study does not offer reimbursement for, or payment of, travel, lodging or meals.

3.5 OFF STUDY CRITERIA

Subjects will be removed from the study for any of the following:

- Completed study follow-up period (16 weeks)
- Participant requests to be withdrawn from study
- Participant becomes too ill to continue participation
- Participant is in need of additional psychotherapeutic support due to significant mental health concerns (e.g., moderate to severe depression or anxiety)
- Inability to consent / loss of capacity
- Lost to follow-up
- Investigator discretion
- Death

3.5.1 Lost to Follow-up

A participant will be considered lost to follow-up if he or she fails to respond to 2 or more timepoint check ins and is unable to be contacted by the study site staff.

The following actions must be taken if a participant fails to return to the clinic for a required study visit:

- The site will attempt to contact the participant and reschedule the missed visit within one week and counsel the participant on the importance of maintaining the assigned visit schedule and ascertain if the participant wishes to and/or should continue in the study.
- Before a participant is deemed lost to follow-up, the investigator or designee will make every effort to regain contact with the participant (where possible, 3 telephone calls and, if necessary, an IRB approved certified letter to the participant's last known mailing address or local equivalent methods). These contact attempts should be documented in the participant's medical record or study file.
- Should the participant continue to be unreachable, he or she will be considered to have withdrawn from the study with a primary reason of lost to follow-up..

4 DATA COLLECTION AND EVALUATION

4.1 DATA COLLECTION

The PI/adjunct PI will be responsible for overseeing entry of data into an in-house password protected electronic system (Labmatrix) and ensuring data accuracy, consistency and timeliness. The principal investigator, adjunct principal investigator, associate investigators/research nurses and/or a contracted data manager will assist with the data management efforts. Primary and final analyzed data will have identifiers so that research data can be attributed to an individual human subject participant.

End of study procedures: Data will be stored according to HHS, FDA regulations and NIH Intramural Records Retention Schedule as applicable.

Loss or destruction of data: Should we become aware that a major breach in our plan to protect subject confidentiality and trial data has occurred, this will be reported expeditiously per requirements in section **5.2.1..**

4.2 DATA SHARING PLANS

4.2.1 Human Data Sharing Plan

Identified or coded, linked data will be shared with approved outside collaborators under appropriate agreements; and de-identified data will be shared at the time of publication and or public presentation.

4.3 TOXICITY CRITERIA

The following adverse event management guidelines are intended to ensure the safety of each patient while on the study. The descriptions and grading scales found in the revised NCI Common Terminology Criteria for Adverse Events (CTCAE) version 4.0 will be utilized for AE reporting. All appropriate treatment areas should have access to a copy of the CTCAE version 5.0. A copy of the CTCAE version 4.0 can be downloaded from the CTEP web site (http://ctep.cancer.gov/protocolDevelopment/electronic_applications/ctc.htm).

5 NIH REPORTING REQUIREMENTS / DATA AND SAFETY MONITORING PLAN

5.1 DEFINITIONS

Please refer to definitions provided in Policy 801: Reporting Research Events found [here](#).

5.2 OHSRP OFFICE OF COMPLIANCE AND TRAINING / IRB REPORTING

5.2.1 Expedited Reporting

Please refer to the reporting requirements in Policy 801: Reporting Research Events and Policy 802 Non-Compliance Human Subjects Research found [here](#).

5.3 NCI CLINICAL DIRECTOR REPORTING

Problems expeditiously reported to the OHSRP in iRIS will also be reported to the NCI Clinical Director. A separate submission is not necessary as reports in iRIS will be available to the Clinical Director.

5.4 NIH REQUIRED DATA AND SAFETY MONITORING PLAN

5.4.1 Principal Investigator/Research Team

The clinical research team will meet on a regular basis when patients are participating in the intervention period on the trial to discuss each dyad. All data will be collected in a timely manner and reviewed by the principal investigator or medical advisory investigator. Events meeting requirements for expedited reporting as described in section **5.2.1** will be submitted within the appropriate timelines.

The principal investigator and medical advisory investigator (when indicated) will review adverse event and study data on each patient to ensure safety and data accuracy. The principal investigator will personally conduct or supervise the investigation and provide appropriate delegation of responsibilities to other members of the research staff.

6 STATISTICAL CONSIDERATIONS

6.1 STATISTICAL HYPOTHESIS

The current protocol is a pilot study, and therefore its primary aim does not include hypothesis testing. Components of feasibility (as described in section **6.1.1**) will be evaluated during the recruitment phase (i.e., proportion of eligible dyads who enroll) and following the 8-week EMI/psychoeducation period.

6.1.1 Primary Objective

The primary objective of this study is to assess the feasibility and acceptability of an enhanced mindfulness intervention in children and young adults (ages 5-24) with a high-grade or high-risk cancer and one of their primary caregivers. Feasibility and acceptability will be evaluated based on the following:

1. Proportion of eligible dyads who enroll during a two-year period
2. Treatment specific retention among all randomized participants, with a target retention rate of 70% over the 8 week EMI/control period
3. Compliance with at-home practices, with a proposed target rate of 4 out of 7 days per week on average over the 8 week EMI period
4. Parent and child reports of satisfaction on the feasibility questionnaire; for youth ages 8+ and caregivers, average item scores >3.0 will be deemed to reflect adequate feasibility

Of note, because the sample size of this study is very limited, even the results of the comparisons tested using statistical methods and identified within the primary objective will be considered descriptive and hypothesis generating.

6.2 SAMPLE SIZE DETERMINATION

Sample size determination was not undertaken for this protocol because it is a small pilot intervention primarily aiming to test the feasibility of the proposed EMI. We specifically aimed to recruit 10 dyads per arm because this sample size would provide enough subjects to yield data appropriate for a pilot study. It is also anticipated that this sample can be recruited within a reasonable amount of time, over a 2 year period (1 to 2 dyads per month, on average). The proposed sample size will likely limit the ability to evaluate preliminary efficacy, which is an exploratory aim.

6.3 POPULATIONS FOR ANALYSES

For the primary outcome of feasibility, all randomized participants will be included. In addition, as described below in section **6.4.2**, we will track total number of eligible individuals approached about the intervention (prior to randomization/enrollment), which will allow us to evaluate the proportion of eligible dyads who enroll. To evaluate exploratory aims, a modified intent-to-treat dataset will be used and will include all participants who, at a minimum, complete the initial in-person training (across EMI and psychoeducation conditions) and questionnaires at Time 1 (baseline) and Time 2 (8 weeks).

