2.6 BASELINE EVALUATION

Following parental consent and child assent, the parent/caregiver (see **Table 1**) and the participant (see **Table 2**) will complete a baseline assessment (Time 1) including questionnaires that assess their stress, emotional (e.g., depression, anxiety) and physical (e.g., pain, fatigue) wellbeing, in addition to baseline mindfulness/self-compassion. Disease parameters (e.g., cancer type and location, treatment history and radiation/chemotherapy doses, steroid use) will be abstracted from medical records. Participants will then be randomized to the enhanced mindfulness intervention (n=10 dyads) or a psychoeducation control group (n=10 dyads). The experimental design is depicted in **Figure 1**.

[figure not shown]

Figure 1 (See the Study Instrument 1 for descriptions of the measures).

2.6.1 Measures assessing caregiver (parent) functioning:

1. Demographic Questionnaire (5 minutes)

(see Study Instrument 1 for additional information regarding measures)

Table 1: Measures assessing parent functioning

Study Variable	Measure	Time Point	Time to Complete (approximate)
Self-compassion	The Self-Compassion Scale	All	10 minutes
Acceptance	Illness Cognition Questionnaire	All	< 5 minutes

Study Variable	Measure	Time Point	Time to Complete (approximate)
Mindfulness skills	Mindful Attention and Awareness Scale (MAAS)	All	5 minutes
Emotional well-being	PROMIS Emotional Distress: Anxiety and Depression, Short Forms 8a	All	5 minutes
Physical well-being	PROMIS Fatigue and Sleep Disturbance, Short Forms 6a	All	< 5 minutes each
Affect	Positive and Negative Affect Scale	All	5 minutes
Coping	Coping Inventory	All	<5 minutes
Feasibility	Feasibility Survey	Post-EMI	5 minutes
Total amount of time at each assessment			~ 35 minutes

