6.4 STATISTICAL ANALYSES

6.4.1 General Approach

For descriptive statistics, categorical data will be presented as percentages. Continuous data will be presented as means with standard deviations and ranges. For inferential statistics, statistical significance will be declared if $\alpha=0.05$ and tests will be two-tailed; results will be interpreted in the context of a pilot study in which statistical testing is for descriptive purposes. For exploratory analyses, checks of assumptions will be conducted and corrective procedures will be applied accordingly (e.g., transformation of non-normal data or nonparametric tests will be substituted).

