6.4.5 Exploratory Analyses

Given the small sample, there may be limited power to detect changes on all exploratory outcome measures. Descriptive and summary statistics will be used to summarize secondary outcome measures between the EMI and control groups. Bivariate analyses (i.e., correlations, chi-square analysis as appropriate) will then be conducted to identify potential covariates for subsequent analyses. Dependent samples t-tests will assess changes pre- to post-intervention in child anxiety, depression, pain behavior, fatigue, mindfulness, and health-related quality of life among youth in the EMI group and also youth in the psychoeducational control group.

In addition, using dependent samples t-tests, we will explore changes pre- to post-intervention in caregiver anxiety, depression, stress, fatigue, sleep disturbance, psychological flexibility, mindfulness, and self-compassion among the intervention group and also parents in the psychoeducational control group. Given the small sample, these analyses will be considered hypothesis generating.

Linear regression models using the 8-week or 16-week assessment as the outcome will be considered in an effort to preliminarily estimate the effect size of the intervention, with

adjustment for potential confounders including scores at baseline. We will assess which demographic (e.g., age), medical, psychological, and environmental factors are related to preliminary efficacy of the intervention.

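### The exploratory modified intent-to-treat set is a completers set: it leaves out randomized participants with usable outcomes and exposes the between-arm estimates to selection

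*Combined protocol and SAP*

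**What the plan says.** Section 6.3 defines two analysis sets. For feasibility, "For the primary outcome of feasibility, all randomized participants will be included". For the exploratory aims, "a modified intent-to-treat dataset will be used and will include all participants who, at a minimum, complete the initial in-person training" in either arm, together with the "questionnaires at Time 1 (baseline) and Time 2 (8 weeks").

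Section 2.6 fixes the order of events. The baseline questionnaires come first, and then "Participants will then be randomized to the enhanced mindfulness intervention (n=10 dyads) or a psychoeducation control group (n=10 dyads"). The in-person session (section 3.2) and Time 2 follow.

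The exploratory objectives in 1.1.2 are worded as changes compared with the psychoeducation control. Section 6.4.5 plans between-arm descriptive summaries, within-arm dependent t-tests and, for the effect size, "Linear regression models using the 8-week or 16-week assessment as the outcome will be considered", adjusted for confounders that include baseline scores. Section 6 gives no method for missing outcomes in these analyses and no all-randomized sensitivity analysis.

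**The concern.** An intent-to-treat label, even a modified one, tells a reader that the groups compared are close to those created by randomization. Here entry depends on two things that happen afterwards, and one of them is having the 8-week outcome.

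The selection is unlikely to be neutral, because the protocol's own reasons for loss are tied to what is measured:

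- Section 3.5 takes participants off study when they become too ill, die, or need further psychotherapeutic support for significant depression or anxiety. Anxiety and depression are exploratory outcomes.
- Section 3.1 lets patients who progress before week 8 and cannot be evaluated be left out of the target number and replaced.
- Section 3.2.2 asks controls for Time 2 only if their physical and psychiatric health has not changed materially. Section 3.1 states no such condition for the EMI arm, so as written the route into the set differs by arm.

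The preliminary effect size is at stake. Section 3.1 presents preliminary efficacy data from a randomized pilot as part of the justification for a larger trial, and section 1.2.3 plans that trial.

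**Working it through.** The plan states no power or bias figure to reproduce. Section 6.2 says "Sample size determination was not undertaken for this protocol because it is a small pilot intervention primarily aiming to test the feasibility of the proposed" intervention, and chooses 10 dyads per arm.

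**1. Which conditions follow randomization.** Time 1 precedes it (2.6), so requiring Time 1 does no harm. The session and Time 2 follow it. That makes two post-randomization conditions.

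**2. Who is dropped with data in hand.** (a) A participant with Time 1 and Time 3 but no Time 2 is outside the set, so the 16-week regression loses an observed outcome. (b) A participant who missed the session but returned Time 1 and Time 2 is outside the set for every exploratory analysis. The documents give no figure for the size of either group.

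**3. How many could be excluded.** Section 6.1.1 assesses retention "with a target retention rate of 70% over the 8 week EMI/control period". At exactly that target, 10 × 0.70 = 7 dyads per arm remain and 20 − 14 = 6 of 20 are excluded while the target is met. This is an illustration, not a forecast. It ignores replacement, and section 3.1 lets a caregiver stay on when the patient leaves.

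**4. Size of a spurious arm difference when the true effect is zero.** Assumptions, none of them in the documents: outcomes are standard normal, the baseline-outcome correlation is 0.5, and dropout removes the highest values of a latent score that correlates c with week-8 distress. If a fraction r is retained, the mean outcome of those retained shifts by −c × φ(z_r)/r, where z_r is the normal quantile of r.

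- r = 0.70: φ(0.524)/0.70 = 0.497
- r = 0.90: φ(1.282)/0.90 = 0.195

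The raw bias is therefore 0.497c if dropout depends on the outcome in one arm only, and (0.497 − 0.195)c = 0.302c if retention is 70% in one arm and 90% in the other. Simulation with 1,000,000 per arm agreed with these and gave the baseline-adjusted values:

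| Scenario | c | Raw (SD) | Baseline-adjusted (SD) |
|---|---|---|---|
| 70% in both arms, same mechanism | 0.3 / 0.5 / 0.7 | about 0 | about 0 |
| 70% in one arm, 90% in the other | 0.3 / 0.5 / 0.7 | 0.09 / 0.15 / 0.21 | 0.07 / 0.12 / 0.17 |
| 70% in both, outcome-related in one arm only | 0.3 / 0.5 / 0.7 | 0.15 / 0.25 / 0.35 | 0.11 / 0.19 / 0.27 |

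The sign follows the arm that loses its more distressed members. Selective loss from EMI flatters the intervention, and selective loss from control hides a benefit.

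**5. Against sampling error.** With the same 0.5 correlation, the residual variance is 1 − 0.25 = 0.75. The adjusted standard error is about √(0.75 × 2/7) = 0.46 SD with 7 per arm, and √(0.75 × (1/7 + 1/9)) = 0.44 SD with 7 and 9. The adjusted biases are therefore about 0.07/0.44 = 0.16 to 0.27/0.46 = 0.59 of a standard error.

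**The case against.** The strongest reply is that the plan already bounds the problem. The primary outcome keeps everyone randomized. Retention is reported overall and by arm (6.4.2), so differential loss will be visible. Section 6.4.1 treats testing as descriptive, 6.4.5 calls its within-arm tests hypothesis generating, and the regressions are only to be considered. The set's criteria are stated openly. All of this stands and keeps the point modest. It does not explain why observed outcomes should be discarded.

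A second reply is that people without Time 2 have nothing to contribute. That holds for the within-arm pre-post tests, which need both assessments by construction and never relied on randomization. It fails for the 16-week regression, and for anyone who skipped the session but returned questionnaires.

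A third is that few people will be affected by the session rule. The session follows the baseline measures, and in the EMI arm it is timed to an existing clinic visit where possible. That is fair. The different session lengths (75 to 90 minutes against about 30 plus 15) do not themselves show different attendance.

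Some stronger readings are tempting but not supported:

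- A reader might infer a bias of 0.50 SD. That needs dropout perfectly correlated with the outcome in one arm and random in the other, and it ignores the planned baseline adjustment. It is a ceiling.
- A reader might infer that the arm comparison is certainly biased. With the same rate and mechanism in both arms the bias is about zero, and the documents give no dropout-outcome correlation.
- A reader might infer that redefining the set repairs the week-8 comparison. It does not. Participants with no follow-up outcome remain unobserved under any definition.

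**Conclusion.** The concern holds as a moderate, inexpensive correction to the exploratory analyses. The set in section 6.3 is a completers set, and it feeds the between-arm summaries and the 8- and 16-week regressions. If dropout differs by arm in rate or mechanism, the spurious baseline-adjusted difference is about 0.07 to 0.27 SD in either direction, under the assumed correlations of 0.3 to 0.7 and the retention patterns shown. If dropout does not differ, the bias is about zero. The wording of 6.3 is certain; the size and direction of any bias are not. The primary feasibility outcome is unaffected, and the within-arm t-tests have no randomization protection to lose.

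Two related matters limit what any analysis set can deliver. Controls are offered the EMI once Time 2 is complete (3.1), so the 16-week contrast is between assigned arms, not between EMI and no EMI. And section 3.2.2 places control Time 2 within a year of baseline, while 3.1 and 6.3 place it at 8 weeks. Because Time 2 defines entry to the set, these sections must be reconciled.

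**What to change.** In section 6.3:

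- Define the main exploratory set as all randomized participants with baseline data, analysed in the assigned arm whether or not they attended the session. Do not require Time 2 for the 16-week model.
- Keep the present set as a sensitivity analysis labelled completers.
- Report exclusions and replaced patients by arm and reason.

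In section 6.4.5:

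- Specify a baseline-adjusted model that uses all available visits, for example a mixed model for repeated measures, so that participants with Time 3 but no Time 2 contribute. State that this reduces but does not remove bias from outcomes that are never observed.
- State that the 16-week contrast compares assigned arms after controls were offered the EMI.

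Reconcile the control Time 2 timing across sections 3.1, 3.2.2 and 6.3.

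The cost is SAP wording and one more model run. The small downside is that a few participants with little exposure to the intervention enter the main estimate.
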